NC1	Somnolence/ Agitation	normal	somnolence or agitation, non-disabling change in activity	somnolence or agitation, requires care-giver	somnolence or agitation, requires institutionalization	coma
NC2	Personality Change	no change	change, not disruptive to pt or family	disruptive to pt or family	harmful to others or self	psychosis
NC3	Convulsions	normal	focal seizure without impairment of consciousness	focal seizure with impairment of consciousness	generalized seizure, tonic-clonic or absence attack	seizure with loss of consciousness > 10 min
NC4	Malaise/ Fatigue/Lethargy	none	mild, able to continue normal activities	change in normal daily activity	in bed or chair > 50% of waking hrs	
NC5	Anxiety/ Depression	normal	mild, able to continue normal activities	change in normal activity	unable to function	suicidal
NC6	Cerebral Necrosis	none	present			
NC8	Neurocortical - Other (specify)		mild	moderate	severe	life-threatening
NC9	CNS - Other (specify)		mild	moderate	severe	life-threatening
NEUROMOTOR						
NM0	Weakness	none or no change	subjective weakness; no objective findings	mild objective weakness without significant impairment of function	objective weakness with impairment of function	paralysis
NM1	Incoordination/ Ataxia	normal	slight incoordination, dysdiadokinesis	intention tremor, dysmetria, nystagmus	locomotor ataxia	
NM2	Speech Impairment	normal		slurred speech	expressive aphasia or severe difficulty communicating	mute
NM3	Cerebellar Necrosis	no	present			
NM8	Neurocerebellar - Other (specify)		mild	moderate	severe	life-threatening
NM9	Neuromotor Other (specify)		mild	moderate	severe	life-threatening

Codes	Toxicity	GRADE				
		0	1	2	3	4
NEUROSENSORY						
NS0	Paresthesia	normal	mild paresthesia	moderate paresthesia, non-disabling	disabling paresthesia (interferes with function)	
NS1	Numbness/ Other PNS	normal		non-disabling objective sensory loss	disabling objective sensory loss	
NS2	Reflexes	normal	diminished reflexes	loss of deep tendon reflexes		
NS3	Hearing	none or no change	asymptomatic, hearing loss on audiometry only	tinnitus	hearing loss interfering with function but correctable with hearing aid	deafness not correctable
NS4	Vision	none or no change		nyctalopia with normal vision in normal light	symptomatic subtotal loss of vision or blurred vision in normal light	blindness
NS5	Taste	normal	slightly altered taste metallic taste	markedly altered taste		
NS9	Neurosensory - Other (specify)		mild	moderate	severe	life-threatening
NEURO - OTHER						
NR0	Headache	none	mild	moderate, or severe but transient	unrelenting and severe	
NR1	Dizziness/Vertigo	none	non-disabling		disabling	
NR2	Insomnia	normal	occasional difficulty sleeping, may require sleeping pills		difficulty sleeping despite medication	
NR3	Restlessness	normal	requires sedation			
NR4	Arachnoiditis	no	yes (also code symptoms)			
NR9	Neuro - Other (specify)		mild	moderate	severe	life-threatening
PAIN						
PA0	Other Pain (specify site)	normal	non-narcotics	oral narcotics	parenteral narcotics	uncontrollable
PA1	Bone Pain	(Same definitions as Other Pain)				
PA2	Tumor Flare (also code Hypercalcemia if it applies)	none	pain requiring non-narcotic or redness or increase in tumor size		(Grade 2 - 5 same definitions as Other Pain)	
PA3	Abdominal Pain	(Same definitions as Other Pain)				
RENAL/BLADDER						
BL0	Incontinence	normal	with coughing, sneezing, etc.	spontaneous, some control	no control	
BL1	Dysuria	none	mild pain	painful or burning urination, controlled by pyridium	not controlled by pyridium	
BL2	Urinary Retention	none	urinary residual > 100cc or occasionally requires catheter or difficulty initiating urinary stream	self catheterization always required for voiding	surgical procedure required (TUR or dilatation)	
BL3	Increased Frequency/Urgency	no change	increase in frequency or nocturia up to 2x normal	increase > 2x normal, but < hourly	with urgency and hourly or more, or requires catheter	
BL4	Hemorrhagic Cystitis	none	blood on microscopic exam	frank blood, no treatment required	bladder irrigation required	requires cystectomy or transfusion (also code hemorrhage)

Codes	Toxicity	GRADE				
		0	1	2	3	4
BL5	Bladder Cramps	none		yes (Code pain if applicable)		
BL9	Bladder - Other (specify)		mild	moderate	severe	life-threatening
RE0	Creatinine	ULN	< 1.5 x ULN	1.5 - 3.0 x ULN	3.1 - 6.0 x ULN	> 6.0 x ULN
RE1	Proteinuria	no change	1+ or < 0.3 g% or < 3 g/l	2 - 3+ or 0.3 - 1.0 g% or 3 - 10 g/l	4+ or > 1.0 g% or > 10 g/l	nephrotic syndrome
RE2	Hematuria	neg	micro only	gross, no clots	gross + clots	requires transfusion (also code hemorrhage)
RE3	Renal failure					dialysis required
RE9	Renal - Other (specify)		mild	moderate	severe	life-threatening
GU0	Ureteral Obstruction	none	unilateral, no surgery required	bilateral, no surgery required	not complete bilateral, but stints, nephrostomy tubes or surgery required	complete bilateral obstruction
GU1	GU Fistula	none			yes	
GU9	GU - Other (specify)		mild	moderate	severe	life-threatening
MISCELLANEOUS						
M00	Alopecia	no loss	mild hair loss	pronounced or total hair loss		
M01	Weight Gain	< 5.0%	5.0-9.9%	10.0-19.9%	20.0%	
M02	Weight Loss	< 5.0%	5.0-9.9%	10.0-19.9%	20.0%	
M03	Laryngitis	normal	mild or intermittent hoarseness	persistent hoarseness, able to vocalize	whispered speech	tracheostomy or intubation
M04	Salivary	normal	mild mouth dryness or slightly thickened saliva	moderate to complete dryness		acute salivary gland necrosis
M05	Anorexia	no	yes			
		(also code Weight Loss if it applies)				
M09	Dehydration	no	dry mucous membranes, diminished skin turgor	requires IV fluid replace- ment (brief)	requires IV fluid replacement (sustained); hospitalization	hypotensive; requires in- tensive care; hemo- dynamic collapse
		(also code applicable cause, if known)				
M07	Wound Dehiscence	no	skin or subcutaneous		fascial	
M08	Wound necrosis	no			yes	
M06	Rectal laceration	no			yes	
M99	Miscellaneous- Other (specify)		mild	moderate	severe	life-threatening

Last Revised 12/94 ds/mb

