- 7.11 In all participants who undergo a surgical procedure in which prostate tissue is removed (e.g., prostate biopsy, TURP, radical prostatectomy), specimens will be submitted to the Pathology Core Laboratory for centralized pathology review in accordance with Section 12.0 and Appendix 19.4. The Pathology Core Laboratory will also serve as the Prostate Tissue Repository for these specimens. Sera for annual PSA determinations will be submitted to the Central Laboratory Facility; residual sera will be banked for future study in a serum bank to be maintained by the Central Laboratory Facility.
- 7.12 The Data and Safety Monitoring Committee will be charged with monitoring and evaluating potential detection bias during the study's progress. This committee may require interim DHT determinations and/or prostate biopsy (in accordance with Section 7.7) in a sample of participants to determine if such bias is operational.
- 7.13 Adherence.

Participant adherence with the medication regimen as well as the follow-up schedule is critical for proper study completion. Data Managers will contact participants every three months for the study's duration to assure medication adherence as well as to reinforce follow-up visit schedules.

Following randomization, tablet counts will occur every six months, i.e., each time the participant requires a new supply of Study Drug. All adherence information will be recorded on study forms. Details of, and procedures for, the assessments are found in the Study Manual.

7.14 Study Blinding Information and Criteria for Removal from Protocol Treatment:

- a. All participants, Study Centers, pathology and laboratory personnel will be blinded to study treatment.
- b. Laboratory and pathology specimens will be labeled by participant identification number and initials only.
- c. Participants treatment will be unblinded only if the treating physician demonstrates a compelling medical need for this information. The study drug may be discontinued without unblinding the participant.
- d. As study arms will be analyzed using an intent to treat method, participants are never "dropped" from the study.
- e. Participants will be removed from protocol treatment under the following circumstances:
  1. diagnosis of prostate cancer.
  2. initiation of treatment for benign prostatic hyperplasia (BPH) with finasteride or other 5-alpha reductase inhibitor.
  3. seven years following randomization (termination of the study).

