**8.0 TOXICITIES TO BE MONITORED AND DOSAGE MODIFICATIONS**

- 8.1 There will be no modifications to the study drug dose.
- 8.2 For decreased libido, impotence and decreased volume of ejaculate or any clinically acceptable symptoms potentially due to the study drug, participants should be requested to remain on study drug. If they refuse, they may be allowed to discontinue the drug. They should then be reassessed in three months. If the side effect has not resolved, the participants can restart the drug. If the side-effects improve, the participants should be re-challenged with the drug and if the side effect recurs, the drug should be discontinued permanently.

The PCPT will not use the new NCI Common Toxicity Criteria for the reporting of Adverse Drug Reactions/Adverse Events and routine follow-up. Please use the Southwest Oncology Group Toxicity Criteria in Appendix 19.1 for: 1) assessment of all symptoms (including those related to sexual function) for the purpose of reporting Adverse Drug Reactions/Adverse Event and for 2) assessment of symptoms not related to sexual function for routine toxicity reporting. For assessment of symptoms of sexual function for eligibility purposes and routine toxicity reporting, use the following criteria in lieu of those in Appendix 19.1.

Impotence:

- Grade 1 decrease in normal function, able with difficulty to achieve vaginal penetration.
- Grade 3 absence of function, no erections

Loss of Libido:

- Grade 1 minimal decrease in desire for sexual activity, no impact on frequency of intercourse
- Grade 2 moderate decrease in desire for sexual activity, minimal impact on frequency of intercourse
- Grade 3 moderate to severe decrease in desire for sexual activity, moderate impact on frequency of intercourse
- Grade 4 no desire for sexual activity, no intercourse

Ejaculate Volume:

- Grade 1 less than 1/3 reduction in ejaculate volume (as perceived by the participant)
- Grade 2 1/3 to 2/3 reduction in ejaculate volume
- Grade 3 greater than 2/3 reduction in ejaculate volume
- Grade 4 no ejaculate

- 8.3 Unexpected or fatal toxicities (including suspected reactions) must be reported to the Southwest Oncology Group Operations Office, and to the IRB. The procedure for reporting adverse reactions is outlined in Section 16.0.

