### Adverse Experiences

Any unexpected or serious adverse experience, if deemed drug related, must be reported within 24 hours to the Southwest Oncology Group Operations Office Adverse Drug Reaction (ADR) representative ([name]), who will obtain information on the ADR. Depending on the nature of the reaction, the ADR representative will advise further. See guidelines on next page. All deaths considered drug-related must be reported immediately to the ADR representative. On double-blinded studies, if the investigator must know what treatment the participant received to make therapeutic decisions, the code for that particular participant can be broken by telephoning the central unblinding number (see Study Manual for more details).

All adverse experiences must also be reported to the Institutional Review Board within 10 days and documentation of this report sent to the Southwest Oncology Group Operations Office.

All adverse experiences must also be recorded in the appropriate section of the case report form. The report should include, whenever possible, the investigator's written medical judgment as to relationship of the adverse experience to study medication(s) (i.e., "probable", "possible" or "unrelated").

GUIDELINES FOR REPORTING OF ADVERSE DRUG REACTIONS (ADRs)/ADVERSE EVENTS (AEs)  
OCCURRING WITH FINASTERIDE ON **SWOG-9217**

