**WITHIN 24 HOURS OF NOTIFICATION OF THE REACTION**

**CALL THE OPERATIONS OFFICE AT [name]**

**WITHIN 10 DAYS, SEND TO THE OPERATIONS OFFICE**

- 1) **A COPY OF THE ADR REPORTING FORM**
- 2) **IRB NOTIFICATION DOCUMENTATION**
- 3) **COPIES OF ALL DATA RECORDS**

All Grades 3 - 5 Unknown Reactions and Grades 4 - 5 Known Reactions according to the Southwest Oncology Group Toxicity Criteria must be reported as ADRs/AEs. All hospital discharge summaries and death certificates will be submitted for evaluation.

**For grading reaction, see Southwest Oncology Group Toxicity Criteria, Section 19.0. Please do NOT use the NCI Common Toxicity Criteria version 2.X for toxicity or adverse event reporting.**

The ADR report should be documented on the Southwest Oncology Group ADR Form and mailed to the following address:

ATTN: ADR Program  
Southwest Oncology Group  
Operations Office  
[name]  
[name]

A list of all known toxicities can be found in either the Drug Information, Background or Informed Consent Form of the protocol.

New diagnoses of cancer, including prostate cancer, in PCPT participants need not be reported as adverse events. However, all diagnosis of cancer must be reported as assessment data in accordance with Section 9.0 and the Study Manual.

Reactions judged definitely not to be treatment related should not be reported. **However, a report shall be submitted if there is only a reasonable suspicion of drug effect.**

Copies of reports of all Grades 3 - 5 Unknown Reactions will be forwarded from the Operations Office to the FDA (using the guidelines provided in the Code of Federal Regulations 21 CFR 312.32), [name], Jr., M.D., DCPC and Merck Research Laboratory.

**Specific Adverse Event Reporting Guidelines for PCPT  
End-of-study Prostate Biopsies**

- Adverse events *related to biopsy* that should be reported:
  1. Bleeding requiring either hospitalization or transfusion
  2. Infection requiring antibiotic therapy
  3. Any hospital admission (include diagnosis and outcome in report)
  4. Death
- If any other biopsy-related event occurs that seems to meet the requirement for reporting according to the protocol adverse event guidelines, call the AE Specialist in the Operations Office [contact]) to discuss.

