## SOUTHWEST ONCOLOGY GROUP TOXICITY CRITERIA

1. Toxicity grade should reflect the most severe degree occurring during the evaluated period.
2. Toxicity grade = 5 if that toxicity caused or contributed to the death of the patient.
3. Do not code if the symptoms are certainly or most likely due to disease or other non-treatment cause.
4. If patient at baseline has Grade 1 or greater, do not code unless patient worsens due to toxicity. If there is worsening, code the level the patient increases to -- do NOT adjust for baseline.
5. Code all toxicities that apply, e.g., for a patient with pneumonitis, code pneumonitis as well as any pulmonary function codes which apply.
6. NCI codes for infection, pulmonary, neuro-sensory, neuro-cortical, neuro-cerebellar, neuro-constipation and skin will be calculated at the Statistical Center from the Southwest Oncology Group codes.
7. Note that for some toxicities certain grades are not defined and may not be coded.
8. Granulocytes/Bands refers to segmented neutrophils plus bands.

		GRADE				
Codes	Toxicity	0	1	2	3	4
HEMATOLOGIC						
HE0	WBC	4.0	3.0 - 3.9	2.0 - 2.9	1.0 - 1.9	< 1.0
HE1	PLT	LLN	75.0 - < LLN	50.0 - 74.9	25.0 - 49.9	< 25.0
HE2	Hgb	LLN	10.0 - < LLN	8.0 - 9.9	6.5 - 7.9	< 6.5
HE3	Granulocytes/ Bands	2.0	1.5 - 1.9	1.0 - 1.4	0.5 - 0.9	< 0.5
HE4	Lymphocytes	2.0	1.5 - 1.9	1.0 - 1.4	0.5 - 0.9	< 0.5
HE9	Hematologic- Other (specify)		mild	moderate	severe	life-threatening
CARDIAC						
CA0	Cardiac- Dysrhythmia	none	asymptomatic, transient requiring no therapy	recurrent or persistent, no therapy required	requires treatment	requires monitoring; or hypotension or ventricular tachycardia, or fibrillation
CA1	Cardiac- EF/CHF	none	asymptomatic, decline of resting ejection fraction by 20% of baseline value	asymptomatic, decline of resting ejection fraction by > 20% of baseline value	mild CHF, responsive to therapy	severe or refractory CHF
CA2	Cardiac- Ischemia	none	non-specific T-wave flattening	asymptomatic, ST and T wave changes suggesting ischemia	angina without evidence for infarction	acute myocardial infarction
CA3	Cardiac- Pericardial	none	asymptomatic effusion, no intervention required	pericarditis (rub, chest pain, ECG changes)	symptomatic effusion; drainage required	tamponade; drainage urgently required
CA9	Cardiac- Other (specify)	mild	moderate	severe	life-threatening	
CIRCULATORY						

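### Appendix 19.1 (rules 3 and 4) lets blinded sites leave symptoms uncoded on a causality judgment, in conflict with Section 16.0; this can dilute the Objective 1.3 comparison for symptoms that no other form captures

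*Supplement*

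**What the plan says.** Four places bear on this.

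- **Section 8.2** assigns Appendix 19.1 to two uses: grading all symptoms for adverse drug reaction (ADR) and adverse event reports, and "assessment of symptoms not related to sexual function for routine toxicity reporting". For sexual symptoms in routine reporting, sites are told to "use the following criteria in lieu of those in Appendix 19.1".
- **Appendix 19.1, rule 3:** "Do not code if the symptoms are certainly or most likely due to disease or other non-treatment cause". **Rule 4**, for a man with Grade 1 or more at baseline: "do not code unless patient worsens due to toxicity".
- **Section 16.0, Adverse Experiences:** "All adverse experiences must also be recorded in the appropriate section of the case report form". Where possible, the report gives the investigator's view of the relationship to study drug as probable, possible or unrelated.
- **Section 16.0, ADR guideline:** "Reactions judged definitely not to be treatment related should not be reported". A reasonable suspicion of drug effect is enough to require a report.

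Under Section 7.14a, "All participants, Study Centers, pathology and laboratory personnel will be blinded to study treatment". Section 11.14 analyses Objective 1.3 (long-term toxicity and side effects) by comparing event rates and effect magnitudes between the arms.

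**The concern.** A rule that codes only toxicity thought to come from treatment makes sense where there is no control group. Here a concurrent blinded placebo arm supplies the background rate. The site's opinion on cause is not needed for the comparison, and a blinded site has little basis for it. An unexpected drug effect that resembles a common complaint of men aged 55 or older is what a site would most naturally ascribe to something else.

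Unexpected effects are a fair thing to plan for. The main human safety data in Section 3.1b come from a study of 322 days' median duration, while this trial treats for seven years. The same section lists hypersensitivity reactions and breast enlargement or tenderness that came to light only after marketing. If rules 3 and 4 govern the analysed data, some cases of such an effect are never counted in either arm, and the contrast between arms shrinks.

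**Working it through.** **1. The rules side by side.**

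| Source | Use | Left out |
|---|---|---|
| App. 19.1 rule 3 | Toxicity coding | Symptoms certainly or most likely of other cause |
| App. 19.1 rule 4 | Coding when baseline grade is 1 or more | Worsening not judged due to toxicity |
| 16.0 Adverse Experiences | Case report form | Nothing; *unrelated* is a permitted label |
| 16.0 ADR guideline | ADR reports | Only definitely unrelated reactions |

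A site that follows rule 3 will seldom have a coded symptom to which *unrelated* could be attached. Rule 3's *most likely* is also a looser ground for exclusion than the ADR guideline's *definitely not*, although Section 8.2 applies Appendix 19.1 to ADR assessment too.

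**2. The plan's own power table (Section 11.11).** Inputs: n = 1,800 per arm, one-sided alpha 1% (z = 2.326). Formula, with d = p2 − p1 and p̄ the mean of p1 and p2:

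power = Φ{ [d − 1/n − z√(2p̄(1−p̄)/n)] / √[p1(1−p1)/n + p2(1−p2)/n] }

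For 2% v 4%: (0.01944 − 2.326 × 0.00569) / 0.00568 = 1.095, so power is .863 against a stated .86. All ten rows reproduce within one percentage point. No stated figure is in dispute.

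**3. Coding only a share c of cases, equal in both arms, at the same settings.** Replace p1 and p2 by c·p1 and c·p2. The documents give no value for c, so a range is shown.

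| Contrast | c = 1 | .75 | .50 | .25 |
|---|---|---|---|---|
| 1 v 2% | .50 | .36 | .22 | .09 |
| 2 v 4% | .86 | .73 | .50 | .22 |
| 5 v 8% | .90 | .77 | .55 | .25 |
| 10 v 13% | .67 | .51 | .32 | .14 |

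The measures named in Section 11.11 are sexual symptoms, graded under Section 8.2. These rows therefore stand for a non-sexual symptom of the same frequency in the first 3,600 men, whose side effects Section 11.13 says are watched most closely.

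**4. The whole trial.** Inputs: n = 9,000 per arm, two-sided 5% (z = 1.960), no continuity correction. The contrasts 5 v 6% and 2.0 v 2.7% are assumptions. For 5 v 6% with every case coded: (0.0100 − 1.960 × 0.003399) / 0.003398 = 0.983, power .84. With half coded (2.5 v 3.0%): (0.0050 − 1.960 × 0.002438) / 0.002438 = 0.091, power .54.

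| Contrast | c = 1 | .50 | .30 | .20 |
|---|---|---|---|---|
| 5 v 6% | .84 | .54 | .35 | .25 |
| 2.0 v 2.7% | .87 | .59 | .39 | .28 |

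**5. Dropping the equal-coding assumption (5 v 6%).** Let b be the share of background cases coded and e the share of drug-caused cases coded. The coded rates are 0.05b on placebo and 0.05b + 0.01e on finasteride.

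| b | e | Coded rates | Power |
|---|---|---|---|
| .50 | .50 | 2.5 v 3.0% | .54 |
| .50 | .70 | 2.5 v 3.2% | .81 |
| .50 | .80 | 2.5 v 3.3% | .89 |
| .20 | .20 | 1.0 v 1.2% | .25 |
| .20 | .50 | 1.0 v 1.5% | .86 |

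Two of these exceed the unfiltered .84. The filter costs power when sites cannot tell drug-caused cases from background, and can gain power when they can.

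**6. Larger contrasts at 9,000 per arm, equal coding.** With only 20% coded, 2 v 4% and 5 v 8% each keep power of about .94. For 1 v 2%, power is .97 at 50% coding and .69 at 20%.

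**The case against.** The strongest reply is that much of the harm data never passes through rule 3.

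- The Study Calendar schedules cardiovascular events, other cancers, BPH and death as outcomes, and urinary symptoms, sexual function and SF-36 as self-report.
- Section 16.0 calls for all hospital discharge summaries and death certificates.
- Section 7.14e has the monitoring committee follow the relative rates of medical events judged not drug-related. Section 11.13 promises it reports of all adverse events, with unblinded review every six months.
- Section 11.14 draws on event reports, interviews and questionnaires, not on Appendix 19.1 codes alone.

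All of this stands. A reader might infer that the whole long-term toxicity comparison is filtered by guesswork; the documents do not support that.

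Second, coding a toxicity and recording an adverse experience may be separate acts. An event could be entered as unrelated and carry no toxicity code. The Study Manual, which holds the forms and is not shown, may settle this. The point limits the conflict but does not remove it: the protocol does not say which record feeds the comparison.

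Third, rule 3 removes only symptoms certainly or most likely of other cause, so doubtful cases are still coded. And the power losses depend on modest contrasts and on equal coding of background and drug-caused cases, as steps 5 and 6 show. Equal coding is plausible for an unexpected effect, but it is not established.

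**Conclusion.** The conflict between Appendix 19.1 (rule 3 and the causality clause of rule 4) and Section 16.0 is in the current text and should be reconciled. Its reach is limited to coded symptoms that are mainly non-hospitalised, non-sexual, non-urinary and non-cardiovascular. Within that group the comparison for Objective 1.3 can be diluted.

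The size cannot be fixed from the documents, because the share of symptoms left uncoded is unknown. Under equal coding of background and drug-caused cases, 5 v 6% at 9,000 per arm drops from .84 to .54 at half coding and .25 at one-fifth. In the first 1,800 per arm, half coding takes 2 v 4% from .86 to .50. With 9,000 per arm and the larger contrasts of step 6, or with better recognition of drug-caused cases, the loss is often small or absent.

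Two stronger readings do not hold. One is that most of any excess is discarded: at 50% equal coding exactly half is lost, and more only if fewer cases are coded. The other is that the filter would create a false difference: with sites blinded it should act alike in both arms when there is no drug effect, so type I error is not inflated, provided recognisable drug effects do not reveal the assignment.

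**What to change.** Section 8.2 already overrides Appendix 19.1 for sexual symptoms, so the change belongs there. State that:

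1. Rule 3 and the causality clause of rule 4 do not apply to routine toxicity reporting in this trial.
2. Every symptom that is new or worse than baseline is graded regardless of presumed cause, with attribution entered in a separate field.
3. Objective 1.3 is compared between arms on all graded events, with treatment-attributed events as a supplementary analysis.

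For ADR reports, bring the *most likely* wording of Appendix 19.1 into line with the *definitely not* threshold in Section 16.0, and check that the Study Manual forms agree.

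The cost is a form field, a training note, and more background symptoms to grade. The side-effect assessments are already scheduled at the six-month and annual visits, so no visit is added.
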